5.3 Lifestyle Considerations

5.3.1 Meals and Dietary Restrictions

Meals and dietary restrictions are not applicable for tarlatamab. For SOC chemotherapy, refer to regional prescribing information and/or relevant local guidelines.

5.3.2 Caffeine, Alcohol, and Tobacco

Caffeine, alcohol, and tobacco limitations are not applicable for tarlatamab. For SOC chemotherapy, refer to regional prescribing information and/or relevant local guidelines.

5.3.3 Activity

Not applicable.

5.4 Subject Enrollment

Before subjects begin participation in any study-specific activities/procedures, Amgen requires a copy of the site's written institutional review board/independent ethics committee (IRB/IEC) approval of the protocol, informed consent form (ICF), and all other subject information and/or recruitment material, if applicable see Section 11.3.

The subject or the subject's legally authorized representative must personally sign and date the IRB/IEC and Amgen approved informed consent before commencement of study-specific procedures.

Each subject who consents to the study receives a unique subject identification number before any study-related activities/procedures are performed. The subject identification number will be assigned by IRT. This number will be used to identify the subject throughout the clinical study and must be used on all study documentation related to that subject.

The subject identification number must remain constant throughout the entire clinical study; it must not be changed after initial assignment, including if a subject is rescreened. This number will not necessarily be the same as the randomization number assigned for the study.

Subjects are eligible to be enrolled in the study when the investigator confirms that the subject has met all eligibility criteria. Subjects are considered enrolled at the time of randomization, defined as successful randomization transaction via IRT. The investigator is to document enrollment decision and date, in the subject's medical record and in/on the Subject Enrollment case report form (CRF) via IRT.

Enrollment into the SOC arm will be monitored in order to ensure an appropriate distribution of subjects into each of the SOC treatments and an appropriate proportion of anti-PD-(L)1 exposed subjects.

Sites that do not enroll subjects within 6 months of site initiation may be closed.

5.5 Screen Failures

Screen failures are defined as subjects who consent to participate in the main clinical study but are not subsequently enrolled in the study. A minimal set of screen failure information will be collected that includes demography, screen failure details, eligibility criteria, medical history, prior therapies, and any serious adverse events.

Individuals who do not meet the criteria for participation in this study (screen failure) may be rescreened up to 2 times. Refer to Section 8.1.1.

6. Study Intervention

Study intervention is defined as any investigational product(s), noninvestigational product(s)/auxiliary medicinal product(s), placebo, combination product(s), or medical device(s) intended to be administered to a study subject according to the study protocol.

Note that according to local regulations in several countries, investigational product(s) described in Section 6.1.1 are referred to as investigational medicinal product(s) and noninvestigational product(s) described in Section 6.1.2 are referred to as non-investigational medicinal product(s).

A summary of the dosing and administration of each treatment is shown in [Table 6-1](#).

6.1 Study Interventions Administered

6.1.1 Investigational Products

Table 6-1. Investigational Products

Study Treatment Name	Amgen Investigational Product:^a
Dosage Formulation	Tarlatamab is supplied as a sterile, single-use, preservative free lyophilized drug product containing 1 or 10 mg of tarlatamab per vial. Tarlatamab is intended for reconstitution with sterile water for injection and dilution in an IV bag with normal saline (0.9% sodium chloride) and an IV solution stabilizer. The drug product is formulated with L glutamic acid, sucrose, polysorbate 80, pH 4.2.
Unit Dose Strength(s)	1 mg step dose on cycle 1 day 1
Dosage Levels and Dosage Frequency	10 mg target dose starting cycle 1 day 8, cycle 1 day 15, and Q2W thereafter
Route of Administration	IV infusion
Accountability	The dose, start date/time, stop date/time, and lot number of tarlatamab, are to be recorded on each subject's eCRF(s).
Dosing Instructions	Tarlatamab will be administered as an IV infusion for 60 minutes (\pm 10 minutes) followed by a slow bolus flush. Investigational products will be administered at the study center by a qualified staff member. A physician must be available at the time of administration of investigational products.

Footnotes defined on last page of this table.

Study Treatment Name	Monitoring Guidance	Amgen Investigational Product: ^a Tariquetamab
		
- Cycle 1 Day 1 and Cycle 1 Day 8:
○ Subject will remain at study site for 6 to 8 hours post-infusion at C1D1 and C1D8. Cohabitant (caregiver) support for 24 hours post-infusion and the ability to stay within 1 hour of a hospital for 24 hours is required.○ Subjects may be discharged after the required monitoring period if there are no signs and symptoms of CRS, ICANS, or other acute toxicities according to the discretion of the treating physician. Counseling the subject and caregiver on signs and symptoms of CRS and ICANS by a health care provider is required prior to discharge.- Subjects return to site on cycle 1 day 2 and cycle 1 day 9 for vital signs and physical examination.- Monitoring for subsequent treatment visits is at the discretion of the investigator if asymptomatic and clinically stable. Consider monitoring if the subject experiences a grade ≥ 2 CRS, any grade ICANS, or any grade ICANS-related neurologic^b adverse events at the immediate prior treatment (ie, following the dose given at the prior visit).- Cycle 2+
○ Additional monitoring may be recommended post-infusion based on occurrence of CRS, ICANS, or ICANS-related neurological events.

In the event of an extended study treatment interruption (see [Table 6-3](#)),

subjects are required to be monitored according to cycle 1 monitoring guidance.

Page 2 of 2

C1D1 = cycle 1 day 1; C1D8 = cycle 1 day 8; CRS = cytokine release syndrome; eCRF = electronic case report form; IV = intravenous; ICANS = immune effector cell-associated neurologic syndrome; Q2W = every 2 weeks.

^a Tariquetamab will be manufactured and packaged by Amgen and distributed using Amgen clinical study drug distribution procedures.

^b ICANS-related neurologic adverse events per discretion of investigator, which may include, but are not limited to: confusion, delirium, encephalopathy, apraxia, ataxia, neurotoxicity, seizure, tremor, dysgraphia, expressive aphasia, depressed level of consciousness, or impaired attention.

6.1.1.1 Standard of Care Treatment Options

In some regions, SOC chemotherapy administered for preventative, diagnostic, or therapeutic reasons, may be considered noninvestigational medicinal products.

6.1.1.1.1 Lurbinectedin

Lurbinectedin will be dosed at the approved regimen of 3.2 mg/m² on day 1 of each 21-day cycle. Lurbinectedin will be administered as an IV infusion for 60 minutes (± 10 minutes).

Where supplied by Amgen, **information regarding** lurbinectedin formulation and dose **preparation will be provided to the site**. Where supplied locally, refer to the regional prescribing information.

The dose, start date/time, and stop date/time are to be recorded on each subject's electronic case report forms (eCRFs). Product lot number will be retained as part of the site level records.

Refer to the regional manufacturer prescribing information for lurbinectedin dosing, dose adjustments, administration and for additional information.

6.1.1.1.2 Topotecan

Topotecan will be dosed at 1.5 mg/m² IV, with the exception of China, which will dose at 1.2 mg/m² IV or other locally approved dose or 2.3 mg/m²/day oral on days 1, 2, 3, 4, and 5 of each 21-day cycle. Topotecan Injection will be administered as an IV infusion over 30 minutes (± 5 minutes). Topotecan capsules should be swallowed whole. Do not chew, crush, or divide capsules. If the dose is missed or vomiting occurs after taking a dose, do not administer an additional dose and take the next dose at the scheduled time.

Topotecan **may be supplied by Amgen or locally supplied by sites**. Where supplied by Amgen, **information regarding topotecan formulation and dose preparation will be provided to the site**. Topotecan capsules are expected to be locally sourced per local practice and regulation. Refer to the regional prescribing information for product details. Subjects will be instructed to take their oral topotecan dose in the clinic after all pre-dose assessments have been performed during day 1 of each cycle. For days 2, 3, 4, and 5 of the cycle, subjects can take their oral topotecan dose at home, if deemed appropriate by the investigator.

The dose, start date/time, and stop date/time are to be recorded on each subject's eCRF(s). Additional dosing information **should** be collected through a web-based diary when subjects self-administer oral topotecan at home. Product lot number will be retained as part of the site level records.

Refer to the regional manufacturer prescribing information for topotecan dosing, dose adjustments, administration and for additional information.

6.1.1.1.3 Amrubicin

Amrubicin will be dosed at the guideline recommended regimen of 40 mg/m² (Guidelines for Diagnosis and Treatment of Lung Cancer in Japan, 2023) and will be administered as an IV infusion over 5 to 15 minutes on days 1 to 3 of each 21-day cycle. Prophylactic use of granulocyte colony-stimulating factor (G-CSF) is allowed, with investigator's discretion.

Where supplied by Amgen, **information regarding amrubicin formulation and dose preparation will be provided to the site.**

The dose, start date/time, and stop date/time are to be recorded on each subject's eCRF(s). Product lot number will be retained as part of the site level records.

Refer to the regional prescribing information for amrubicin dosing, dose adjustments, administration and for additional information.

6.1.2 Noninvestigational/Auxiliary Medicinal Products

In some regions, the investigational product(s) and/or noninvestigational product(s)/auxiliary medicinal product(s) described in Section [6.1.1.1](#) and administered for preventative, diagnostic, or therapeutic reasons, may be considered noninvestigational medicinal products.

All other noninvestigational product(s)/auxiliary medicinal product(s) including, tarlatamab pre- and post-infusion medication (dexamethasone and IV hydration) and standard of care (SOC) chemotherapy co-medications, that are commercially available are not provided by Amgen (except if required by local regulation). The investigator will be responsible for obtaining supplies of these noninvestigational product(s)/auxiliary medicinal product(s).

6.1.3 Medical Devices

Noninvestigational medical devices may be used in the conduct of this study as part of standard care.

Non-Amgen noninvestigational medical devices (eg, syringes, sterile needles), that are commercially available are not usually provided by Amgen (except, for example, if required by local regulation). The investigator will be responsible for obtaining supplies of these devices.

6.1.3.1 Tarlatamab Pre- and Post-infusion Medications

Dexamethasone

Dexamethasone 8 mg IV (or equivalent dose of other corticosteroids) will be administered within 1 hour prior to tarlatamab infusion on days 1 and 8 of cycle 1.

IV Hydration

Prophylaxis with IV hydration (1 L normal saline over 2 to 4 hours) will be administered immediately following tarlatamab doses on cycle 1 day 1 and day 8.

6.1.3.2 Standard of Care Co-medications

Refer to the regional prescribing information or institutional guidelines (if not addressed in prescribing information) for additional information regarding SOC co-medications.

6.1.3.3 Cytokine Release Syndrome Rescue Medication

All sites will ensure that CRS rescue medications are available on-site, including corticosteroids and (for sites in regions where tocilizumab is approved and available) sites are required to have tocilizumab or siltuximab (if tocilizumab is not available) on site for potential treatment of CRS **prior to dosing subjects in the Tarlatamab arm.**

Refer to the regional prescribing information or institutional guidelines (if not addressed in prescribing information) for additional information regarding rescue medication.

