3	
 Fever^b: $\geq 38^{\circ}\text{C}$ WITH 
 Hypotension: requiring a single vasopressor (excluding vasopressin) AND/OR^c 
 Hypoxia: requiring high-flow nasal cannula^d, facemask, nonrebreather mask, or Venturi mask 	
 Delay tariquetamab until event improves to CRS grade ≤ 1. 	
 Administer: 
 Symptomatic treatment (eg, paracetamol/acetaminophen) for fever Supplemental oxygen (high-flow nasal cannula [$> 6 \text{ L/min}$]), facemask, non-rebreather mask, or Venturi mask), as needed A vasopressor \pm vasopressin, as needed Dexamethasone (or equivalent) IV at a dose maximum of 3 doses of 8 mg (24 mg/d). The dose should then be reduced step-wise. 
AND/OR
 
 Consider use of tocilizumab (in countries where available) as an additional therapy in this setting at a dose of 4-8 mg/kg as a single dose. Tocilizumab can be repeated for an additional 3 doses with at least an 8-hour interval between doses. 	
 The next infusion may be administered if all of the following criteria are met: 
 The Amgen medical monitor must be consulted prior to resuming treatment The event has resolved to grade ≤ 1 prior to resuming treatment 
In case of infusion interruption, continue treatment with next scheduled infusion. Do not resume prior infusion or administer delayed infusion.
 
In the case of 2 separate grade 3 CRS events.
	
 If there is no improvement to CRS \leq grade 2 within 5 days and CRS \leq grade 1 within 7 days. OR If CRS grade 3 occurs at the step dose. OR As per local institutional guidelines.

Abbreviations and footnotes defined on last page of table.

Table 6-2. Tariquetamab Dose Modification Guidelines for Adverse Events

Grade	Description of Severity ^a	Interrupt/Delay	Specific Management	Restart guidance	Permanent Discontinuation
Cytokine Release Syndrome continued (see Section 11.11.1 for additional guidance and grading scale details)					

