3 (cont)			
Monitor:
 
 CRS symptoms including temperature, blood pressure, and pulse oximetry Fluid status, maintain IVF as needed Consider chest X-ray and obtaining appropriate cultures to rule out infection If refractory hypotension (after 2 fluid boluses), consider ECHO 
Admit to intensive care unit for close clinical and vital sign monitoring per institutional guidelines
		
4	
Life-threatening symptoms
 
 Fever^b: ≥ 38°C WITH Hypotension: requiring multiple vasopressors (excluding vasopressin) AND/OR^c Hypoxia: requiring positive pressure (eg, CPAP, BiPAP, intubation, and mechanical ventilation) 	
Immediately stop any ongoing infusion
	
Administer:
 
 Symptomatic treatment (eg, paracetamol/acetaminophen) for fever Supplemental oxygen (positive pressure (eg, CPAP, BiPAP, intubation, and mechanical ventilation), as needed Multiple vasopressors, as needed Dexamethasone (or equivalent) IV at a dose maximum of 3 doses of 8 mg (24 mg/d). Further corticosteroid use should be discussed with the Amgen medical monitor. Tocilizumab should be administered at a dose of 4-8 mg/kg as a single dose. Tocilizumab can be repeated for an additional 3 doses with at least an 8 hour interval between doses 	
Do not resume tariquetamab.
	
Permanently discontinue tariquetamab

Abbreviations and footnotes defined on last page of table.

Table 6-2. Tarlatamab Dose Modification Guidelines for Adverse Events

Grade	Description of Severity ^a	Interrupt/Delay	Specific Management	Restart guidance	Permanent Discontinuation
Cytokine Release Syndrome continued (see Section 11.11.1 for additional guidance and grading scale details)					

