4 (cont)			
If tocilizumab is not available, siltuximab (an anti-IL-6 monoclonal antibody) may be used in the management of CRS, following the criteria outlined in this table. The recommended dose of siltuximab is 11 mg/kg administered over 1 hour as an IV infusion, consistent with the prescribing information for the treatment of multicentric Castleman's disease (Sylvant Prescribing Information), and the CARTOX Working Group Guidelines for CRS management (Neelapu et al, 2018). Siltuximab may be repeated if needed, in the event that CRS recurs after a subsequent infusion of tarlatamab. Siltuximab may not be repeated in an individual subject who develops anaphylaxis to siltuximab, or gastrointestinal perforation after siltuximab. 
Monitor:
 
CRS symptoms including temperature, blood pressure, and pulse oximetryFluid status, maintain IVF as neededConsider chest X-ray and obtaining appropriate cultures to rule out infectionIf refractory hypotension (after 2 fluid boluses), consider ECHO 
Admit to intensive care unit for close clinical and vital sign monitoring per institutional guidelines.
		

Abbreviations and footnotes defined on last page of table.

Table 6-2. Tarlatamab Dose Modification Guidelines for Adverse Events

Grade	Interruption/Delay	Specific Management	Restart guidance	Permanent Discontinuation
Tumor Lysis Syndrome (TLS) – Grading according to Common Terminology Criteria for Adverse Events (CTCAE v5.0) (see Section 11.11.3)				
Present	Immediate interruption/delay until event has improved to grade ≤ 1	
TLS should be managed according to the local SOC and institutional guidelines.
 
• Resume only if successfully managed and improvement to \leq grade 1 in ≤ 14 days• Consult with Amgen medical monitor.• In case of infusion interruption, continue treatment with next schedule infusion, do not resume prior infusion or administer delayed infusion.• Monitoring: per Monitoring Guidance for first tarlatamab administration (Section 6.1.1)	
If subject missed more than 2 consecutive doses of tarlatamab
 
OR
 
In case of repeat TLS event, or life-threatening TLS, permanently discontinue tarlatamab.
	

Abbreviations and footnotes defined on last page of table.

Table 6-2. Tarlatamab Dose Modification Guidelines for Adverse Events

Grade	Interruption/Delay	Specific Management	Restart guidance	Permanent Discontinuation

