ACTH = adrenocorticotrophic hormone; BiPAP = bi-level positive airway pressure; CARTOX = CAR-T-cell-therapy-associated TOXicity; CRS = cytokine release syndrome; CPAP = continuous positive airway pressure; CT = computed tomography; ECG = electrocardiogram; EOT = end of treatment; FSH = follicle-stimulating hormone; FT4 = free T4; G-CSF = granulocyte colony-stimulating factor; GI = gastrointestinal; ICANS = immune effector cell-associated neurologic syndrome; ICU = intensive care unit; IGF-1 = insulin-like growth factor 1; IL-6 = interleukin 6; IV = intravenous; IVF = intravenous fluid(s); LH = luteinizing hormone; MRI = magnetic resonance imaging; N/A = not applicable; NSAIDS = non-steroidal anti-inflammatory drugs; OR = objective response; PS = performance status; Q2 = every 2; RT-PCR = real time polymerase chain reaction; SARS-CoV-2 = severe acute respiratory syndrome coronavirus 2; SOC = standard of care; TLS = tumor lysis syndrome; TSH = thyroid-stimulating hormone

^a American Society for Transplantation and Cellular Therapy (ASTCT) grading system for CRS (Lee et al, 2019).

^b Fever is defined as temperature $\geq 38^{\circ}\text{C}$ not attributable to any other cause. In subjects who have CRS then receive antipyretic or anticytokine therapy such as tocilizumab, siltuximab, or steroids, fever is no longer required to grade subsequent CRS severity. In this case, CRS grading is driven by hypotension and/or hypoxia.

^c CRS grade is determined by the more severe event: hypotension or hypoxia not attributable to any other cause. For example, a subject with temperature of 39.5°C , hypotension requiring 1 vasopressor, and hypoxia requiring low-flow nasal cannula is classified as grade 3 CRS.

^d Low-flow nasal cannula is defined as oxygen delivered at ≤ 6 L/minute. Low flow also includes blow-by oxygen delivery, sometimes used in pediatrics. High-flow nasal cannula is defined as oxygen delivered at > 6 L/minute.

^e For neutropenia adverse events grade ≤ 2 , please follow institutional guidelines for management.

^f Based on Immune Effector Cell Therapy Toxicity Assessment and Management (also known as CARTOX)
<https://www.mindanderson.org/documents/for-physicians/algorithms/clinical-management/cytokine-release-web-algorithm.pdf>

^g Per CTCAE 5.0

For all other treatment interruptions or delays, re-start tarlatamab in accordance with the following guidelines in [Table 6-3](#):

Table 6-3. Step-dose Rechallenge Requirement After Tarlatamab Delay

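### The CRS rescue rules leave two gaps: no stated duty to stock an anti-IL-6 agent in regions without tocilizumab, and siltuximab text whose grade scope is unclear and whose repeat-use clause sits in the row that stops tarlatamab

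*Protocol*

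**What the plan says.** **Stocking.** Protocol Section 6.1.3.3 opens with a duty on every site to have CRS rescue medication on site, with corticosteroids given as an inclusion. It then adds a requirement that must be met before tarlatamab-arm subjects are dosed and that is conditional on region: "for sites in regions where tocilizumab is approved and available) sites are required to have tocilizumab or siltuximab (if tocilizumab is not available". A second paragraph refers sites to regional prescribing information or institutional guidelines for further information.

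**Use at grade 4.** In Table 6-2 (Section 6.2.2.1) the grade 4 CRS row states "Tocilizumab should be administered at a dose of 4-8 mg/kg as a single dose". Its continuation says that, if tocilizumab is not available, siltuximab "may be used in the management of CRS, following the criteria outlined in this table". The same cell adds: "Siltuximab may be repeated if needed, in the event that CRS recurs after a subsequent infusion of tarlatamab". The restart column for grade 4 rules out resumption, and the last column reads "Permanently discontinue".

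**Use at grade 3.** The grade 3 row reads "Consider use of tocilizumab (in countries where available) as an additional therapy in this setting" and does not mention siltuximab. Its restart column allows further dosing: "The next infusion may be administered if all of the following criteria are met".

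**Elsewhere.** Footnote b of Table 6-2 refers to "anticytokine therapy such as tocilizumab, siltuximab, or steroids", but only to explain how CRS is graded once such treatment has been given. Section 6.1.5 lists tocilizumab and siltuximab among products the sponsor may provision, for the purpose of product complaints. Section 11.11.1 points back to Table 6-2 and to regional or institutional guidance.

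**The concern.** There are two separate inconsistencies.

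First, the stocking rule and the treatment table attach the fallback to different situations. The table names siltuximab for the case where tocilizumab cannot be had. The stocking rule applies only in regions where tocilizumab can be had. A site elsewhere could comply with Section 6.1.3.3 as written and dose a patient with neither agent on the premises.

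Second, the siltuximab text sits in one grade row, but its repeat-use sentence makes sense only for a patient who goes on to receive more tarlatamab. No patient does so after grade 4 CRS. A site treating grade 3 CRS without tocilizumab cannot tell from the table whether the siltuximab text applies to it.

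At stake is the safety of tarlatamab-arm patients with severe CRS and the consistency of rescue treatment across about 240 sites. A smaller consequence concerns the SAP, Section 5.4.4.2, which plans summaries of CRS treated with tocilizumab, CRS duration and use of interventions. Those tables would be harder to interpret if sites read the rescue rules differently.

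**Working it through.** The plan gives no figure to reproduce on this point. The check is a side-by-side reading, followed by a short calculation for scale.

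**Step 1: which sites must hold which agent.** Three situations are possible:

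- *Region with tocilizumab, drug in stock.* Section 6.1.3.3 is met by tocilizumab, and grade 4 of Table 6-2 can be followed as written. No gap.
- *Region with tocilizumab, local shortage.* Section 6.1.3.3 requires siltuximab instead, and grade 4 of Table 6-2 permits siltuximab. The two agree.
- *Region without tocilizumab.* The regional condition in Section 6.1.3.3 is not met, so the named requirement does not apply. The general duty to hold rescue medication remains, but no anti-IL-6 agent is specified. Grade 4 of Table 6-2 still calls for tocilizumab and names siltuximab when it is unavailable. Here the two do not meet.

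**Step 2: can the repeat-use clause operate where it is placed?** It requires (a) an earlier use of siltuximab, (b) a later tarlatamab infusion and (c) recurrent CRS. After a grade 4 event, the same row excludes (b). The clause therefore cannot operate after the event whose row contains it.

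**Step 3: where could it operate?** After grade 3 CRS, (b) is possible, because the restart column allows another infusion if its criteria are met. But the grade 3 row names only tocilizumab, limited to countries where it is available. Whether (a) is contemplated at grade 3 depends on whether the reference in the grade 4 cell to management of CRS under the table's criteria is meant to reach beyond that row. The protocol does not say.

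**Step 4: does any other section settle it?** Footnote b concerns grading. Section 6.1.5 shows that sponsor supply of siltuximab is contemplated but does not say where it must be held. Section 11.11.1 refers back to the table. None states the stocking duty in regions without tocilizumab or the grades that the siltuximab text covers.

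**Step 5: scale.** Protocol Section 4.4 reports CRS at 10 mg in Study 20200491: 1 of 133 subjects at grade 3 and none at grade 4.

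- Grade 3: 1/133 = 0.8%; Clopper-Pearson two-sided 95% upper limit 4.1%.
- Grade 4: 0/133; upper limit 1 − 0.025^(1/133) = 2.7%.

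These describe severe CRS in that study as a whole, not at sites without tocilizumab. The documents do not say how many of the roughly 240 sites, if any, are in such regions, so an expected number of affected patients cannot be derived.

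**The case against.** The strongest reply is that the texts are incomplete rather than contradictory. Much of that stands.

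- A reader might infer that sites without tocilizumab need hold corticosteroids only. The documents do not support this: the opening duty covers rescue medication generally, and corticosteroids are an inclusion, not the whole list.
- A reader might infer that Section 6.1.3.3 contradicts itself by requiring siltuximab only where it is least needed. Unavailability can mean a local shortage in a region that normally has tocilizumab, and on that reading the sentence is coherent. It still says nothing specific for regions without the drug.
- A reader might infer that Table 6-2 makes siltuximab stocking mandatory. It does not. Siltuximab is permitted, not required, and the grade 4 cell also lists corticosteroids, vasopressors, ventilatory support and intensive care.
- A reader might infer that siltuximab is confined to grade 4. The wording about management of CRS under the table's criteria suggests wider scope, which would make the repeat clause workable after grade 3. The grade 3 row does not say so, which leaves an ambiguity of placement.
- The table did not extract cleanly, so exact cell position should be read with some caution. Nothing shows that the siltuximab text was displaced.
- Some regional variation is written into the protocol, through the country qualifier at grade 3 and the deference to local guidance. Not every difference between sites would come from this wording.

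The stocking gap and the unstated grade scope remain after these points are granted.

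**Conclusion.** The point holds as two wording gaps that bear on safety and are cheap to close. Section 6.1.3.3 states no duty to hold an anti-IL-6 agent in regions without tocilizumab, although Table 6-2 names a fallback for that situation. The siltuximab text has unclear grade scope, and its repeat clause presupposes dosing that its own row forbids.

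The practical size is uncertain. Severe CRS was rare in the cited phase 2 data, and the number of sites affected is not given and could be small. The conclusion assumes that the on-site requirement is to be read as written and that the siltuximab text sits where the extracted table shows it.

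No effect on OS, power or type I error is claimed. The CRS summaries in the SAP are descriptive, with no formal hypothesis testing (SAP Section 5.2), and any distortion of them is possible rather than shown. No view is taken on which clinical rule is right.

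**What to change.** Reconcile Section 6.1.3.3 with Table 6-2, with the sponsor's safety team deciding the clinical content:

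1. Make the region condition and the fallback condition in Section 6.1.3.3 agree. State whether the fallback named in Table 6-2 must be on site before tarlatamab dosing where tocilizumab is unavailable.
2. State which CRS grade rows the siltuximab text governs.
3. Place the repeat-use sentence so that it is consistent with the discontinuation rule of the row in which it stands.

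The cost is a wording change in one section and one table, which could be issued to sites as a safety clarification. The possible downside is having to stock a fallback drug at some sites. No analysis changes.
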